1. PROTOCOL SUMMARY

1.1. Synopsis

Name of Sponsor/Company:

Santen Inc.

[name]

Name of Investigational Product:

STN1013600 Ophthalmic Solution

Name of Active Ingredient:

Ursodiol, Ursodeoxycholic acid (UDCA)

Title of Study: OPSIS: A Phase IIa, Randomized, Double-Masked, Placebo-Controlled, Parallel-Group, Multicenter Study Assessing the Efficacy and Safety of STN1013600 Ophthalmic Solution 0.1% and 0.3% Compared with Placebo in Subjects with Presbyopia

Protocol Number: 101360002IN

Number of Subjects (Planned): Approximately 75 subjects with Presbyopia.

Study Center(s): Approximately 13 Sites in the United States

Study Period: Approximately 6 months	Phase of Development: Phase IIa		
Study Objectives and Endpoints:			
Study Objectives	Corresponding Study Endpoints		
Primary Efficacy Objective: To assess the efficacy of two concentrations of STN1013600 ophthalmic solution (0.1% and 0.3%) twice daily dosing when compared to Placebo in subjects aged from 47 to 55 years with presbyopia.	 Primary Efficacy Endpoint: Mean change from baseline in Binocular DCNVA at Month 2 		

Secondary Efficacy Objective:	Secondary Efficacy Endpoints:
To assess the dose response of STN1013600 ophthalmic solution.	 Mean change from baseline in Study Eye DCNVA at all visits
	 Mean change from baseline in Binocular DCNVA at all visits
	• Proportion of subjects who improve 1/2/3-lines or more in Study Eye and Binocular DCNVA at each visit
	• Mean change from baseline in quality of life assessed with Near Activity Visual Questionnaire (NAVQ) at Month 2 and Month 3
	• Subject treatment satisfaction as assessed by Patient Global Rating of Treatment at Month 2
Safety Objective:	Safety Endpoint:
To assess the safety of two concentrations of STN1013600 ophthalmic solution (0.1% and 0.3%) twice daily dosing when compared to Placebo in subjects aged from 47 to 55 years with presbyopia.	 Safety of STN1013600 will be assessed by adverse events (AEs), Intra-ocular Pressure (IOP), slit-lamp bio-microscopy, ophthalmoscopy, and laboratory tests (serum chemistry, hematology, and urinalysis).

Duration of Treatment: 2 months, and 1 month of follow up without treatment.

Methodology:

This is a Phase IIa, randomized, double-masked, placebo-controlled, parallel-group study assessing the efficacy and safety of STN1013600 ophthalmic solution (0.1% and 0.3%) in subjects with Presbyopia.

Subjects with Presbyopia who meet all eligibility criteria at Visit 1 (Screening) will be randomized at Visit 2 (Baseline) to receive treatment for 2 months.

Approximately 75 subjects who meet all eligibility criteria at Visit 1 (Screening) will be randomized at Visit 2 (Baseline) in a 2:2:1 ratio to one of the following three treatment arms:

- 0.1% STN1013600 ophthalmic solution BID (08:00 & $20:00 \pm 60 \text{ min}$)
- 0.3% STN1013600 ophthalmic solution BID (08:00 & 20:00 ± 60 min)
- Placebo (Vehicle) BID ($08:00 \& 20:00 \pm 60 \min$)

Subjects will be treated for 2 months, followed by a 1-month safety follow-up without treatment.

Study Design: (Refer to Figure 1)

This study will consist of a Screening Period of up to 15 days, followed by a 2-month Treatment Period and subsequently 1-month Treatment-free follow-up Period.

At the Visit 1 (Screening), subjects will be screened against the inclusion and exclusion criteria and if subject meets all eligibility criteria, subjects will proceed to Visit 2 (Baseline).

Per study design, subjects who qualify per eligibility criteria will be treated bilaterally (both eyes).

The study eye will be the eye that qualifies with the worse DCNVA per eligibility criteria at Visit 2. If both eyes have the same DCNVA, the right eye will be designated as the study eye.

Treatment Period (2 months):

At Visit 2 (Baseline), approximately 75 eligible subjects will be randomized to receive either 0.1% STN1013600 ophthalmic solution BID or 0.3% STN1013600 ophthalmic solution BID or Placebo BID in a 2:2:1 ratio. Subjects will be treated for 2 months with scheduled assessment visits at

At Visit 2 (Baseline), subjects will administer their first dose of study medication (study eye drops) as per their assigned/randomized study treatment at 20:00 (\pm 60 min). The next day (Day 2), subjects will subsequently dose with their assigned study medication at 08:00 & 20:00 (\pm 60 min) and continue dosing through Visit 6 (Month 2).

Treatment-free Follow-up Period (1 month):

After Treatment Period, subjects will be followed for 1 month with scheduled study assessment (including safety assessments) visits at Visit 7 (Month 3).

Pharmacogenomics/Genomics:

Not applicable

The verning

Santen Steering Committee:

An internal Santen steering committee (SSC) whose members will not be participating in the OPSIS study conduct will serve as an advisory board to the Santen senior management team.

charter.

Masking:

This is a double-masked study. The subjects, Investigators, Examiners and Santen personnel involved in the conduct of the study will be masked to the study treatments. An authorized unmasked study staff member at the investigator site who is not the Investigator or Examiner will dispense and collect study medication(s). Patient medication compliance diary will be reviewed.

Subjects will be instructed not to show the bottles or discuss the eye drops to either the Masked Investigator or the Masked Examiner or other study subjects.

Inclusion criteria:

Participants are eligible to be included in the study only if all of the following criteria apply:

- 1.
- 2. Phakic presbyopic subjects, Male or Female between 47 and 55 years of age.
- Distance-corrected near visual acuity (DCNVA) for each eye, as well as for binocular vision, 70 EDTRS letters or worse (equivalent to 0.3 logMAR or worse; or 20/40 Snellen or worse) at 40 cm. To be reconfirmed at Visit 2 (Baseline).
- 4. Best-corrected distance visual acuity (BCDVA) for each eye of 85 ETDRS letters or better (equivalent to 0.00 logMAR or better; or 20/20 Snellen or better) at 4 m. To be reconfirmed at Visit 2 (Baseline).

5.			

Investigational Product:

0.1% STN1013600 ophthalmic solution contains 0.1% STN1013600.

0.3% STN1013600 ophthalmic solution contains 0.3% STN1013600.
Vehicle:
The vehicle is identical to the investigational product but does not contain the active ingredient STN1013600.
Route of Administration of Investigational Product: Topical ocular
Statistical methods:
An interim analysis may be performed when the first 40 subjects complete Day 14 Visit. There are two goals for this interim analysis: (1) to assess for futility and (2) to assess for efficacy. More details on the interim analysis plan will be provided in the SAP.

Version 1.0 23SEP2022

1.2. Schema

1.3. Schedule of Assessments (SoA)

Table 2:Schedule of Assessments

			T	reatment Peri	od		Follow Up Without Treatment
Study Procedures	Visit 1 / Screening Up to 15 days Before Day 1	Visit 2 Baseline / Day 1	Visit 3 Day 7 + 2 Days	Visit 4 Day 14 + 2 Days	Visit 5 Month 1 + 3 Days	Visit 6 Month 2 + 3 Days	Visit 7 Month 3 + 3 Days/ Early Discontinuation
Informed consent ^a	X						
Inclusion and Exclusion criteria	Х	Х					
b							
Ь							
Demographic information	X						
Ocular and systemic medical history	X						
Vital Signs (Blood Pressure, Heart Rate, Temperature)	Х	X	Х	Х	X	X	Х
Height and weight	Х						
Previous and current concomitant ocular and systemic medications	Х	X	X	X	X	X	Х
Distance Corrected Near Visual Acuity Test (40 cm) ^d	Х	X	Х	Х	X	X	Х
d							

Follow Up Without **Treatment Period** Treatment Visit 1 / Visit 7 Month 3 Screening Visit 2 Visit 3 Visit 4 Visit 5 Visit 6 + 3 Days/ Early Up to 15 Days Baseline / Day 7 Day 14 Month 1 Month 2 **Study Procedures Before Day 1** Day 1 + 2 Days + 2 Days + 3 Days + 3 Days Discontinuation Best Corrected Distance Visual Acuity Test Х Х Х Х Х Х Х (4m)^d Х Х Slit lamp biomicroscopy Х Х Х Х Х Pupil size Х Х Х Х Х Х Х Intraocular Pressure (IOP) Х Х Х Х Х Х Х Х Х Х Х Х Хg Хg Ophthalmoscopy Patient global rating of treatment Х Post-Study Clinical Trial Experience Х Survey Х Х Х Urine pregnancy test (women of childbearing potential only)^h Blood Chemistry and Hematology (CBC, Х Х Х CMP) Hemoglobin A1c Х

Table 2: Schedule of Assessments (Continued)

а

		Treatment Period			Follow Up Without Treatment		
Study Procedures	Visit 1 / Screening Up to 15 Days Before Day 1	Visit 2 Baseline / Day 1	Visit 3 Day 7 + 2 days	Visit 4 Day 14 + 2 days	Visit 5 Month 1 + 3 days	Visit 6 Month 2 + 3 days	Visit 7 Month 3 + 3 Days/ Early Discontinuation
Urinalysis	X				X	X	
Adverse events (AEs)	X	Х	X	Х	Х	Х	Х

Table 2: Schedule of Assessments (Continued)

^h Urine pregnancy test (women of childbearing potential only) may be repeated at each visit as per request of IRB/IECs or at the Investigator's discretion.

ⁱ Only patients fulfilling eligibility criteria will be enrolled and receive the study medication.

2. INTRODUCTION

2.1. Background

Presbyopia refers to a condition in which the accommodative function of the eye gradually decreases with age, making it difficult to focus on close objects. Presbyopia is a common visual system condition in which the aging eye gradually develops impairment in the ability to focus on near and intermediate objects, starting around 40 years of age (Stokes et al., 2022).

Santen is developing STN1013600 (DE-136), a formulation of Ursodeoxycholic Acid (UCDA) as an ophthalmic solution for the treatment of presbyopia. This study is being conducted to evaluate the safety and efficacy of STN1013600 ophthalmic solution in subjects with presbyopia.

This Phase IIa study 1013600IN (OPSIS) will evaluate the efficacy and safety of ophthalmic solution of DE-136 0.1% and 0.3% administered BID for the treatment of Presbyopia.

2.2. Study Rationale

In 2015, an estimated 1.1–1.8 billion people worldwide were impacted by presbyopia, and the number is predicted to reach 2.1 billion by 2030 (Stokes et al., 2022). Until recently the treatment and management options for presbyopia were either optical techniques, *e.g.*, spectacles and contact lenses, or surgical interventions, *e.g.*, laser in-situ keratomileusis (Presby LASIK), corneal inlay, and multi-focal intraocular lenses. However, these options have disadvantages, including reduced visual quality at one or more distances (Charman, 2014) and the risks associated with surgical intervention. Hence, there is an unmet need for a noninvasive treatment that is effective in restoring accommodative function and providing good vision at all distances (Grzybowski et al., 2020).

Pharmacological treatment for presbyopia has the potential to address this unmet need. Two different classes of drugs have been investigated for this purpose. The recent approval in 2021 of VUITY[®] (pilocarpine hydrochloride ophthalmic solution) represents the first in this class of miotics. These drugs increase the depth of focus by decreasing pupil size, creating a pinhole effect.

The long-term outcome on efficacy, safety, and acceptance of VUITY as a standard of care remains to be evaluated.

The other class of drugs in development for presbyopia postulates that lens stiffening and loss of flexibility result in decreased distortion of the lens during accommodation. Although various factors may contribute to the lowering of accommodative function, sclerosis of the lens via oxidation-induced disulfide bonds between the crystalline lens protein seems to be a significant factor (Rowen, 2020, Wolffsohn et al., 2019). Garner et al. found that the antioxidant lipoic acid, reduced disulfide bonds in lens proteins of aged mice and increased lens elasticity in a

concentration-dependent manner. Further, synthesized choline esters were shown to improve the translocation of lipoic acid to the aqueous humor for a more efficient effect (Garner et al., 2016).

2.3. Benefit/Risk Assessment

3. OBJECTIVES AND ENDPOINTS

Table 3:Objectives and Endpoints

Objectives	Endpoints
Primary Efficacy Objective:	Primary Efficacy Endpoint:
To assess the efficacy of two concentrations of STN1013600 ophthalmic solution (0.1% and 0.3%) twice daily dosing when compared to Placebo in subjects aged from 47 to 55 years with presbyopia.	• Mean change from baseline in Binocular DCNVA at Month 2
Secondary Efficacy Objective:	Secondary Efficacy Endpoints:
To assess the dose response of STN1013600 ophthalmic solution.	• Mean change from baseline in Study Eye DCNVA at all visits
	• Mean change from baseline in Binocular DCNVA at all visits
	• Proportion of subjects who improve 1/2/3-lines or more in Study Eye and Binocular DCNVA at each visit
	• Mean change from baseline in quality of life assessed with Near Activity Visual Questionnaire (NAVQ) at Month 2 and Month 3
	• Subject treatment satisfaction as assessed by Patient Global Rating of Treatment at Month 2

Table 3:Objectives and Endpoints (Continued)

4. STUDY DESIGN

4.1. Overall Design

This is a Phase IIa, randomized, double-masked, placebo-controlled, parallel-group study assessing the efficacy and safety of STN1013600 ophthalmic solution (0.1% and 0.3%) in subjects with Presbyopia.

Approximately 75 subjects who meet all eligibility criteria at Visit 1 (Screening) will be randomized at Visit 2 (Baseline) in a 2:2:1 ratio to one of the following three treatment arms:

- 0.1% STN1013600 ophthalmic solution BID (08:00 & $20:00 \pm 60 \text{ min}$)
- 0.3% STN1013600 ophthalmic solution BID ($08:00 \& 20:00 \pm 60 \min$)
- Placebo (vehicle) BID ($08:00 \& 20:00 \pm 60 \min$)

If both eyes of a subject qualify for the study, then the eye with the worse DCNVA will be determined as the study eye. If DCNVA in both qualifying eyes is the same, then the right eye should be designated as the study eye.

Subjects will be treated for 2 months, followed by 1 month safety follow-up without treatment. The total duration of participation for each subject is expected to be approximately 15 weeks.

4.2. Scientific Rationale for Study Design

The purpose of this phase IIa study is to evaluate the safety and efficacy of 2 doses of STN1013600 in subjects with presbyopia. The randomized, placebo-controlled, parallel-group study design is standard for the demonstration of efficacy and safety in multiple-arm clinical trials. The study is randomized and double masked to minimize bias and to reduce the risk of a placebo effect.

4.3. Justification for Dose

4.4. End of Study Definition

A participant is considered to have completed the study if he/she has completed all phases of the study including Month 3 Visit.

The end of the study is defined as the date of the last visit of the last participant in the study.

5. STUDY POPULATION

Prospective approval of protocol deviations to recruitment and enrollment criteria, also known as protocol waivers or exemptions, is not permitted.

5.1. Inclusion Criteria

Participants are eligible to be included in the study only if all of the following criteria apply:

- 2. Phakic presbyopic subjects, Male or Female between 47 and 55 years of age
- 3. Distance-corrected near visual acuity (DCNVA) for each eye, as well as for binocular vision, 70 EDTRS letters or worse (equivalent to 0.3 logMAR or worse; or 20/40 Snellen or worse) at 40 cm. To be reconfirmed at Visit 2 (Baseline).
- 4. Best-corrected distance visual acuity (BCDVA) for each eye of 85 ETDRS letters or better (equivalent to 0.00 logMAR or better; or 20/20 Snellen or better) at 4 m. To be reconfirmed at Visit 2 (Baseline).

5.

5.2. Exclusion Criteria

Participants are excluded from the study if any of the following criteria apply:

Ocular Conditions

- 16. Secondary cause of presbyopia in either eye as assessed by investigator (*e.g.*, damage to lens, zonules or ciliary muscle, multiple sclerosis, cardiovascular accidents, vascular insufficiency, myasthenia gravis, anemia, influenza, measles).
- 17. Any history of ocular surgery (including ocular laser surgery) in either eye or plan of ocular surgery (including ocular laser surgery) during the course of the study.
- 18. Prior invasive therapy for presbyopia (*e.g.*, ciliary body electrostimulation, corneal implants).
 - Prior medical therapy for Presbyopia (*e.g.*, supplements, miotic medications, training exercises) within 30 days of Visit 1 (Screening)
 - Subjects with prior non-surgical optical correction (*e.g.*, corrective eyeglasses) are eligible for the study

5.3. Contraception Requirements

5.4. Screen Failures

Screen failures are defined as subjects who consent to participate in the clinical study but are not subsequently randomly assigned to a study medication/entered in the study.

6. STUDY INTERVENTION

6.1. Study Medications Administered

Table 4:Descriptions of Study Medications

ARM Name	STN1013600, 0.3%	STN1013600, 0.1%	Placebo
Intervention Name	STN1013600	STN1013600	Placebo
Туре	Drug	Drug	Drug
Dose Formulation	Ophthalmic Solution	Ophthalmic Solution	Ophthalmic Solution
Unit Dose Strength(s)	0.3%	0.1%	Not Applicable
Dosage Level(s)	One drop, BID, both eyes throughout the 2-month Treatment Period	One drop, BID, both eyes throughout the 2-month Treatment Period	One drop, BID, both eyes throughout the 2-month Treatment Period
Route of Administration	Topical ocular	Topical ocular	Topical ocular
Use	Experimental	Experimental	Placebo- comparator
IMP and NIMP	IMP	IMP	IMP

ARM Name	STN1013600, 0.3%	STN1013600, 0.1%	Placebo

Table 4:Descriptions of Study Medications (Continued)

6.2. Preparation/Handling/Storage/Accountability

6.2.1. Study Medication Storage

6.2.2. Study Medication Administration

During the Double-Masked Treatment Period, subjects will instill one drop of study medication in each eye at approximately $08:00 \pm 60$ min and $20:00 \pm 60$ min daily from Visit 2 (Baseline) to Visit 6 (Month 2).

6.2.3. Study Medication Accountability

The Principal Investigator is responsible for ensuring that an inventory is conducted upon receipt of the clinical supplies.

6.2.4. Study Medication Handling and Disposal

6.3. Measures to Minimize Bias: Randomization and Masking

This is a double-masked study.

6.4. Study Intervention Compliance

To obtain reliable efficacy and safety data, the following precautions will be taken to ensure compliance with the study medication during the study:

• Subjects will receive verbal and written instructions for proper instillation of the study medication, the dosing regimen, and the conditions of the study medication storage.

• Subjects may be discontinued from the study at the discretion of the investigator if the subject cannot be brought into compliance.

A record of the number of kit cartons dispensed to and taken by each subject must be maintained and reconciled with study medication and compliance records. Medication start and stop dates, including dates for medication delays and/or dose reductions will also be recorded on the CRF.

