7. DISCONTINUATION OF STUDY INTERVENTION AND PARTICIPANT DISCONTINUATION/WITHDRAWAL

7.1. Discontinuation of Study Intervention

It may be necessary for a participant to permanently discontinue (definitive discontinuation) study intervention. If study intervention is definitively discontinued, study assessments should be completed per SoA including Exit Visit. All efforts should be made to complete an early discontinuation exit visit. If study medication is definitively discontinued and the subject has an AE related to study medication, he/she will remain in the study to be evaluated until the resolution of the AE. See the SoA for data to be collected at the time of discontinuation of study intervention and follow-up and for any further evaluations that need to be completed.

Discontinuation of study intervention for any safety concern should be considered if the investigator believes that it is in best interest of the participant.

If a clinically significant finding is identified (including, but not limited to clinically significant changes from baseline in any laboratory evaluation) after enrollment, the investigator or qualified designee will determine if the participant can continue in the study and if any change in participant management is needed. Any new clinically relevant finding should be reported as an AE.

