7.2. Participant Discontinuation/Withdrawal from the Study

• A participant may withdraw from the study at any time at his/her own request or may be withdrawn at any time at the discretion of the investigator for safety, behavioral, compliance, or administrative reasons. This is expected to be uncommon.

- At the time of discontinuing from the study, if possible, an early discontinuation visit should be conducted, as shown in the SoA. See SoA for data to be collected at the time of study discontinuation and follow-up and for any further evaluations that need to be completed.
- The participant will be permanently discontinued both from the study intervention and from the study at that time.
- If the participant withdraws consent for disclosure of future information, the sponsor may retain and continue to use any data collected before such a withdrawal of consent.
- If a participant withdraws from the study, he/she may request destruction of any samples taken and not tested, and the investigator must document this in the site study records.

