8.1.6. Double-Masked Treatment Period, Visit 6 (Month 2)

- •
- Measure vital signs
- Update concomitant medications and procedures/therapies
- •

- •
- Measure vital signs
- Update concomitant medications and procedures/therapies

- Perform slit-lamp Biomicroscopy
- Measure pupil size
- Measure Intraocular Pressure
- •
- •
- Obtain urine and perform a urine pregnancy test if the subject is a female of child-bearing potential.
- Assess for adverse events
- Exit the subject from the study.

NOTE:

If the study medication administration is discontinued, then to the extent possible, all procedures for Study Exit/Early Termination as per SoA (Table 2) will be performed on the day of early termination. Subjects who are discontinued from the study early will not be replaced.

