# 4.4. Analysis Visit and Analysis Window

*Analysis visit* is a timing variable to be used for analyses involving visits. For each analysis visit, an *analysis window* is set up to determine the analysis visit to which a measurement should be mapped (Table 4). The analysis visit of a measurement will be determined based on the study day of the measurement and specified analysis windows and is not necessarily the same as the

study visit at which the measurement was collected. For example, an out-of-window measurement collected at the Day 7 study visit will be mapped to the Day 14 analysis visit, if the study day of the measurement falls into the analysis window of Day 14.

The following *analysis windows* will be applied to minimize the amount of missing data for analysis purposes:

		Analysis Window				
Analysis Visit (Target Study Day)	Protocol Visit Window			Patient Global Rating of Treatment	Blood Chemistry, Hematology, Urinalysis	Other Parameters
Baseline (Day 1)	[1, 1]			NA*	[-,1]	[-,1]
Day 7 (Day 7)	[5, 9]	-		NA*	NA*	[2, 11]
Day 14 (Day 14)	[12, 16]	-		NA *	$\mathrm{NA}^*$	[12, 23]
Month 1 (Day 30)	[27, 33]	-		NA*	[2, 49]	[24, 49]
Month 2 (Day 60)	[57, 63]			[2, -]	[50, -]	[50, day of Month 2 Visit]
Month 3 (Day 90)	[87, - ]			NA*	NA*	[day of Month 2 Visit + 1, - ]

Table 4:Analysis Visit and Analysis Window

\*Not collected at this visit.

If there are two or more visits that fall into the same analysis window, then the visit closest to the target assessment day will be selected for that visit window. In the case that two visits are equidistant to the target assessment day, i.e., one is before and one is after the target assessment day, the latter will be selected for that visit.

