# 5.2. Handling of Missing Data

#### 5.2.1. Efficacy Measures

The primary analysis of DCNVA will be based on observed cases; hence, missing data will not be imputed. As a sensitive analysis of the primary efficacy endpoint, an analysis using mixed-effect model for repeated measures (MMRM) will be performed. The MMRM model will be applied using observed cases and no imputation will be needed.

For continuous secondary endpoints where MMRM-based analysis will be performed, no imputation will be necessary. For binary secondary endpoints with response status, the analysis will be based on observed cases; hence, no imputation will be performed.

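### Removal from the study for non-compliance can cost a subject the Month 2 DCNVA, so the observed-case primary analysis can select on adherence; the likely effect is small and cheap to prevent

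*Protocol*

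**What the plan says.** **Removal.** Protocol 6.4: "Subjects may be discontinued from the study at the discretion of the investigator if the subject cannot be brought into compliance". Protocol 7.2 repeats the ground: a participant "may be withdrawn at any time at the discretion of the investigator for safety, behavioral, compliance, or administrative reasons". It adds "This is expected to be uncommon" and then "The participant will be permanently discontinued both from the study intervention and from the study at that time". An early discontinuation visit is to be held if possible; its column in the Schedule of Assessments includes DCNVA.

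**Stopping drug only.** Protocol 7.1: "If study intervention is definitively discontinued, study assessments should be completed per SoA including Exit Visit". The note closing the exit-visit text in Protocol 8.1 instead has the exit procedures done, as far as possible, on the day of early termination when study medication is discontinued. It adds: "Subjects who are discontinued from the study early will not be replaced".

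**Analysis.** SAP 5.2.1: "The primary analysis of DCNVA will be based on observed cases; hence, missing data will not be imputed". SAP 10.2 says this replaced multiple imputation, because masked review found under 5% of subjects with missing data. SAP Table 4 gives the Month 2 window for DCNVA as "50, day of Month 2 Visit". SAP 8.2.3 adds an MMRM on all observed visits, introduced as a check for prior-data conflict, and a repeat of the primary analysis in the Per-Protocol Set (PPS).

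**The concern.** Compliance is observed after randomization. It may reflect tolerability or a perceived lack of benefit, and either may differ by dose. If poor compliance can end follow-up, it can also decide who has a Month 2 value. The primary comparison would then lean towards subjects who took their drops, and would no longer describe all treated subjects. A Month 2 measurement that was never taken cannot be replaced later, and the placebo arm has only 15 subjects, so each loss there is 1/15 = 6.7% of the arm. The SAP already handles adherence in two places that need no loss of follow-up: the PPS (6.3) and the compliance summary (7.7).

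**Working it through.** **Step 1. Does removal lose the Month 2 value?** Under SAP Table 4, a DCNVA maps to Month 2 only from Day 50. An exit measurement before Day 50 maps to an earlier visit. From Day 50 on it might count, but the window closes on the day of the Month 2 visit, and no upper limit is given for a subject who never has one. A subject removed before Day 50 stays in the Full Analysis Set (FAS) if any post-baseline DCNVA exists, yet adds nothing to the primary comparison.

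**Step 2. Do the sensitivity analyses cover it?** The MMRM keeps the subject's earlier visits and relies on missing at random. The PPS is a subset of the FAS, so the PPS repeat cannot bring these subjects back.

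**Step 3. The plan's power figure.** Inputs from SAP 3.3, 8.2.1 and 8.2.2: difference 4 letters, SD 6, 30 vs 15 subjects, historical control n = 23 with SD 4.35, success if the posterior probability exceeds 0.95. Stated power: at least 81.5%.

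- *No borrowing.* SE = 6 × √(1/30 + 1/15) = 1.897. Power = Φ(4/1.897 − 1.645) = 67.8%.
- *With borrowing.* The text supplied gives no value for the power parameter w, so 81.5% cannot be confirmed. Assume a known SD and a true control mean equal to the historical mean. The placebo data then carry weight a = (15/36) / (15/36 + 23w/4.35²). Solving for 81.5% gives w = 0.211, an effective 4.9 borrowed subjects, and a = 0.619. Posterior SD = √(36/30 + a × 36/15) = 1.639; sampling SD = √(36/30 + a² × 36/15) = 1.456. Power = Φ((4 − 1.645 × 1.639)/1.456) = 81.5%. With no true effect, Φ(−1.645 × 1.639/1.456) = 3.2%.

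**Step 4. How many subjects?** 5% of 75 is 3.75, so fewer than 5% means at most 3, from all causes and pooled over arms. Spread 2:2:1, that is 1.2, 1.2 and 0.6 per arm.

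**Step 5. Bad case.** Assume all 3 are compliance removals from one active arm, and that they would have changed g letters less than those kept. Bias = (3/30) × g. The documents give no g; 2 to 6 letters is an assumption. For 27 vs 15 without borrowing, SE = 6 × √(1/27 + 1/15) = 1.932. With borrowing, the posterior SD is 1.679 and the sampling SD is 1.501.

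| g (letters) | Bias (letters) | False positive, no borrowing: Φ(bias/1.932 − 1.645) | False positive, w = 0.211: Φ((bias − 1.645 × 1.679)/1.501) |
|---|---|---|---|
| no loss | 0 | 5.0% | 3.2% |
| 2 | 0.2 | 6.2% | 4.4% |
| 4 | 0.4 | 7.5% | 5.8% |
| 6 | 0.6 | 9.1% | 7.5% |

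The biases are 5% to 15% of the 4-letter target. SAP 10.2 accepts a type I error up to 0.10; every entry is below it.

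**Step 6. Losses from placebo.** With 3 of 15 lost, the bias is 0.4 to 1.2 letters in either direction. It favours active drug only if the removed placebo subjects would have done better than those kept. In that direction the false-positive rate is 4.0% to 7.4% at w = 0.211. Without borrowing it is 7.4% to 14.5%, but that is not the planned analysis.

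**Step 7. Power after random loss.** With borrowing, power falls from 81.5% to 79.5% (27 vs 15) or 79.3% (30 vs 12), about 2 points. Without borrowing it falls from 67.8% to 66.5% or 62.1%.

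**The case against.** The case against is mainly about size, and most of it stands. The rule is discretionary, investigators are masked, and the protocol expects withdrawal to be uncommon. Missing data from all causes are under 5%. Step 5 stacks three unfavourable assumptions: every missing subject is a compliance removal, all are in one arm, and all would have done worse. SAP 7.1 already tabulates discontinuations by treatment and by primary reason, so an imbalance in compliance removals would show. The MMRM gives partial cover through the earlier visits, and a late exit DCNVA might count as Month 2. The trial is exploratory and sized on feasibility.

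A reader might infer that the primary result is materially biased, or that the false-positive rate is out of control. The documents do not support either: they report no compliance removals, no arm difference and no outcome gap, and the planned borrowing lowers the rates. A reader might also infer that subjects should stay in the study unless they withdraw consent. That would collide with the safety, behavioral and administrative grounds in 7.2, which are not in question here.

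What remains is that the protocol allows outcome collection to end because of adherence, its own sections disagree on assessment after drug stops, and no planned analysis is aimed at this kind of loss.

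**Conclusion.** The concern holds as a modest design weakness. Protocol 6.4 and 7.2 allow a study-level exit for non-compliance; 7.1 expects assessments to continue once drug is stopped; the exit note points to a visit on the day of termination. Together with the Day 50 window and the observed-case rule, this lets adherence after randomization decide who enters the primary analysis.

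The expected effect is small. In the assumed active-arm case the bias stays at or below 0.6 letters and the false-positive rate below the SAP's 0.10 tolerance, and power with borrowing falls by about 2 points. These figures rest on SD 6, an assumed 2-to-6-letter gap, a back-solved w, and a true control mean equal to the historical one. Selection matters more than power, and the case for acting rests on low cost rather than on demonstrated harm.

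**What to change.** 1. Reconcile Protocol 6.4, 7.1, 7.2 and the exit-visit note so that non-compliance alone does not end outcome collection. Non-compliant subjects who are still willing are asked to attend the scheduled visits through the Month 2 DCNVA and are analysed in the FAS as randomized.
2. Handle adherence through the PPS and the SAP 7.7 compliance summary. Dosing decisions, and the safety, behavioral and administrative grounds for withdrawal, stay as written; the change concerns data collection only.
3. For subjects already removed, show compliance removals by arm in the SAP 7.1 disposition table. The SAP already cites masked disposition data, so for this trial the reporting step may be the part that still helps.

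Cost: a protocol amendment with IRB/IEC approval and a note to sites. No new visits are needed. A few poorly compliant subjects would stay in the FAS and slightly dilute the estimate.
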